# **11.2** Subject demographics and other baseline characteristics

All data for background and demographic variables will be listed by treatment group and subject. Summary statistics will be provided by treatment group.

Relevant medical history, current medical conditions, results of laboratory screens, drug tests and any other relevant information will be listed by treatment group and subject. A summary of the steroid dose (prednisone) assigned at the start of the treatment phase and of the prior immunosuppressant therapy will be provided too.

### 11.3 Treatments

Data for study drug administration, rescue medication and concomitant therapies (including steroid dose) will be listed by treatment group and subject.

### 11.4 Analysis of the primary variable(s)

The primary aim of the study is to compare the effect of CMK389 versus placebo on the clinical disease activity of sarcoidosis patients as measured by the change from baseline in the percent predicted FVC at week 16 in the PD population. This will be assessed regardless by the background steroid dose and assuming all patients remained on their treatment throughout the study.

#### 11.4.1 Primary Variable(s)

The primary variable will be the change from baseline in percent predicted FVC after 16 weeks from the first dose of the study drug.

#### 11.4.2 Statistical model, hypothesis, and method of analysis

The change from baseline in percent predicted FVC will be analyzed using a Bayesian model for repeated measurements. The model will investigate effects for treatment by time (included as a class variable) interaction, baseline FVC by time interaction, prior sarcoidosis immunosuppressant therapy (stratification factor) and baseline prednisone dose. The correlation among the repeated measures collected on the same subject will be assessed via an unstructured covariance matrix. The stratification factor may be removed in case of strata with low sample sizes impacting on the convergence of the model.

Uninformative priors will be utilized to obtain the posterior estimates. Baseline is defined as Day 1.

The posterior probability that CMK389 is better than placebo in terms of change from baseline in percent predicted FVC at 16 weeks will be calculated. If it is at least 90%, it will be considered a sign of efficacy of CMK389 in this patient population.

The primary analysis will include all available data from patients in the PD analysis set with baseline and at least one post baseline assessment.

A supplementary analysis may be conducted including also FVC values collected after a change of the background therapy not based on the CSD algorithm.

Novartis	Confidential	Page 83
Amended Protocol Version v08 (Clean)		Protocol No. CCMK389X2201

If data permits, additional subgroup analysis of the primary endpoint will be conducted for the following three subgroups: increased, no change and decreased prednisone dose at week 16 compared to baseline.

#### 11.4.3 Handling of missing values/censoring/discontinuations

Estimates of the missing values will be derived by the model under the missing at random (MAR) assumption. Alternative assumptions may be explored to investigate the robustness of the results under plausible non-missing at random situations.

#### 11.4.4 Summary statistics of safety

All information obtained on adverse events will be displayed by treatment group and subject.

The number and percentage of subjects with adverse events will be tabulated by body system and preferred term with a breakdown by treatment. A subject with multiple adverse events within a body system is only counted once towards the total of this body system.

The number (and proportion) of subjects with AEs of Special Interest (Section 9.1) will be summarized by treatment.

### 11.4.5 Summary statistics of pharmacokinetics

Not applicable

### 11.4.6 Sensitivity analyses

The impact of the changes in steroid dose may be investigated performing two sensitivity analyses. In the first one all FVC data following an increase of the steroid dose will be set to missing and estimated via the model assuming MAR. In the second analysis a penalty will be applied to all the data following an increase of the steroid dose. Further details will be included in the statistical analysis plan (SAP).

# 11.5 Analysis of secondary variable(s)

#### 11.5.1 Efficacy / Pharmacodynamics

Data from other secondary variables will be listed and summarized. Graphical representations over time will be presented. Models similar to the one described for the primary analyses will be carried-out to investigate treatment difference for the continuous variables collected at each visit of the treatment epoch. Pulmonary physiology scores will be analyzed via ANCOVA model for repeated measures, while the percentage of subjects that, at Week 16, deteriorate (defined as: relative reduction from baseline in FVC  $\geq 10\%$  or in FEV1  $\geq 10\%$  or in DLCO  $\geq 15\%$  or relative of 6MWD  $\geq 50$  m) and the percentage of subjects who increased the steroid dose at least one time during the treatment epoch, will be analyzed using logistic regression. This analysis will be carried out if at least 20% of the subjects will show a deterioration/increase of the steroid dose.

The [F]FDG-PET/CT imaging data will be analyzed to identify the maximum standardized uptake values in the following categories:

• A maximum of 10 focal nodal uptake regions (mediastinal, hilar)

Page 84

- A maximum of 10 focal regions of uptake in lung parenchyma •
- A maximum of 10 extra-thoracic focal uptake regions on the whole body scan ٠

F]FDG-PET/CT mean uptake in the reference tissue:

• A region of lung parenchyma, unaffected by focal lesion uptake

The mean of the SUVmax (resp. SUVmean) for each category will be taken to obtain one SUVmax value (resp. SUVmean) per patient / time point / category.

The mean percent change from baseline in SUVmax in the lymph nodes after 16 weeks of treatment will be analyzed using ANCOVA with baseline SUVmax and baseline steroid doses as covariates, and treatment and prior sarcoidosis immunosuppressant therapy as factors.

The same analysis as for the percent change from baseline in SUVmax in the lymph nodes will be performed for the percent change from baseline in SUVmax in the lung parenchyma and the extra-thoracic regions, where available. It will also be repeated for SUV mean in the parenchyma.

The correlation between changes from initial FDG-PET scan in SUVmax and changes from baseline in FVC, FEV1 and 6MWT distance will be assessed with graphical methods.

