## 2.2 Secondary objective(s)

Secondary objective(s)	Endpoints related to secondary objective(s)

 
To assess the impact of CMK389 on steroid use (mg days)
 
	
 
Difference in steroid usage for each arm of the study between baseline and end of treatment
 

 
To assess the impact of CMK389 on a composite index of pulmonary physiology and exercise capacity
 
	
 
Proportion of patients who deteriorate from baseline to Week 16, defined as: relative reduction in FVC ≥ 10% or relative reduction in FEV1 ≥ 10% or relative reduction of DLCO ≥ 15% or relative reduction of 6MWD ≥ 50 m
 

Secondary objective(s)	Endpoints related to secondary objective(s)

 
To explore the impact of CMK389 observed with [F]-fluorodeoxyglucose positron emission tomography/computed tomography ([F]-FDG-PET/CT) imaging
 
	
 
Change in [F]-FDG-PET/CT (SUVmax and SUVmean) from baseline and Week 16
 

 
To assess the pharmacokinetics of

	
 
Pharmacokinetic parameters (Cmax/End of

CMK389	infusion, Ctrough) of CMK389

 
To assess the safety and tolerability of

	
 
Adverse events, vital signs and routine safety

CMK389	laboratory results.

 
To assess the impact of CMK389 on pulmonary physiology
 
	• Change in forced expiratory volume in one second (FEV1) and diffusion capacity for carbon monoxide (DLCO) between baseline and Week 16

 
To assess the impact of CMK389 on

	
 
Change in 6-minute walk distance (6MWD)

exercise capacity	between baseline and Week 16

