1.1 Scope of document

The RAP documents contain detailed information to aid the production of Statistics & Programming input into the Clinical Study Report (CSR) for trial "CCM389X2201".

The Statistical analysis plan (SAP) describes the implementation of the statistical analysis planned in the protocol.

Tables, Figures, Listings (TFL) details the presentation of the data, including shells of summary tables, figures and listings, and Programming Datasets Specification (PDS) contains programming specifications e.g. for derived variables and derived datasets, to support the creation of CSR outputs.

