6.1.3 Statistical model, assumptions and hypotheses

The change from baseline in percent predicted FVC will be analyzed using a Bayesian model for repeated measurements including data collected at weeks 4, 8, 12 and 16. The model will investigate effects for treatment by time (included as a class variable) interaction, baseline percent predicted FVC by time interaction and will include the covariates prior sarcoidosis immunosuppressant therapy (stratification factor) and baseline prednisone dose. Uninformative priors for all the parameters will be utilized to obtain the posterior estimates. The correlation among the repeated measures collected on the same subject will be assessed via unstructured covariance matrix. The stratification factor may be removed in case of strata with low sample sizes impacting on the model fit. Baseline FVC and prednisone will be centered and standardized before used in the model

Commercially Confidential Information

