6.2.2 Descriptive analyses

All secondary variables will be listed by treatment, subject and visit/time. Descriptive statistics will be provided by treatment and visit/time for all continuous variables. Summary statistics will include arithmetic mean, SD, CV (arithmetic), median, minimum and maximum. Summary statistics for ancillary data (oxygen saturation, and vital signs data) collected during the 6 minute walking test will be provided too.

Il-18 and IL-18bp concentrations will be listed and summarized by treatment producing outputs mirroring the ones provided for the PK analysis of CMK389 concentrations but including the results observed in the placebo group.

Clinical status evaluation data (see section 3.1 of the study protocol) will be listed and summarized by treatment and visit. The summary table will report for each component (6MWT distance, FVC, FEV1, MMRC dyspnea score) the corresponding evaluation (Better, Same, Worse) and the overall evaluation.

Subjects who deteriorate at Weeks 4, 8, 12 and 16 and subjects with any increase in steroids for any reason (algorithm driven or not) during the treatment epoch will be summarized, separately, by treatment group using frequency tables.

The correlation between percent changes from baseline [18F]-FDG-PET/CT scan in SUVmax and changes from baseline in FVC, FEV1 and 6MWT distance will be assessed with scatterplot grids. As we may not be able to assume normality of the data, Kendall's tau-b coefficients and its corresponding p-values will be displayed to assess correlation.

Data on new lesions from [18F]-FDG-PET/CT will be only listed.

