6.2.3 Statistical model, assumptions and hypotheses

[¹⁸F]-FDG-PET/CT

The mean percent change from baseline in SUVmax in the nodules and lung parenchyma at week 16 will be analyzed using ANCOVA with baseline SUVmax and baseline steroid doses as covariates and treatment and prior sarcoidosis immunosuppressant therapy as factors.

The same analysis as for the percent change from baseline in mean SUVmax in the nodules and lung parenchyma will be performed for the percent change from baseline in SUVmax in extrathoracic regions, where available, at week 16. It will also be repeated for SUVmean in the three categories.

The same sensitivity and subgroup analyses as the primary may also be performed, if deemed necessary.

A bar chart plot of the percent change from baseline with the corresponding SE will be provided.

Composite index of pulmonary physiology and exercise capacity /steroid dose

A logistic regression model with baseline steroid doses as a covariate and treatment and prior sarcoidosis immunosuppressant therapy as factors, will be applied to patients showing at least a deterioration (as determined by Composite index of pulmonary physiology and exercise

capacity- section 6.2.1) during the treatment period and to patients with at least one steroid dose increase (for any reason - algorithm mediated or just related to an investigator's decision).

Bar chart plots representing the percentage of patients with at least a deterioration during the course of the trial/ with at least one steroid increase during the course of the trial will be provided by treatment.

Key Pulmonary function tests and 6MWD

FVC (in litres), FEV1, FEV1/FVC, PEF, DLCO, DLCO adjusted for hemoglobin, CPI, 6MWD and distance saturation product changes from baseline will be analyzed using the same analysis as defined in Section 6.1.3 but under a frequentist approach (no prior will be applied). The same sensitivity and subgroup analyses as the primary may also be performed, if deemed necessary.

Model based means with corresponding standard errors (SE) by treatment and time will be used to visualize the results over time. A change from baseline of 0 will be assumed at baseline.

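### The protocol's 20% event condition makes the deterioration and steroid-increase comparisons less likely to be run the better the drug works, and the SAP leaves the condition out without revoking it

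*Protocol*

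**What the plan says.** Protocol 2.2 lists deterioration as a secondary endpoint: "Proportion of patients who deteriorate from baseline to Week 16, defined as" a fall beyond a set threshold in any one of FVC, FEV1, DLCO or 6-minute walk distance. Steroid use is also a secondary objective.

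Protocol 11.5.1 sends the proportion deteriorating at Week 16 to logistic regression. For steroids, "the percentage of subjects who increased the steroid dose at least one time during the treatment epoch, will be analyzed using logistic regression". It then sets the condition: "This analysis will be carried out if at least 20% of the subjects will show a deterioration/increase of the steroid dose". The sentence names no arm and no denominator (randomised or evaluable). It gives no reason for 20%, and no alternative analysis if the condition fails beyond the general listing and summary.

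SAP 6.2.3 specifies "A logistic regression model with baseline steroid doses as a covariate and treatment and prior sarcoidosis immunosuppressant therapy as factors". It counts at least one deterioration "during the treatment period and to patients with at least one steroid dose increase", so any visit qualifies and not only Week 16. It does not mention the 20% condition and names no method for sparse events. The one fallback the SAP writes for a model, "The stratification factor may be removed in case of strata with low sample sizes impacting on the model fit", sits in 6.1.3 under the primary FVC analysis, and small strata trigger it rather than few events.

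SAP 6.2.2 keeps an unconditional description: deteriorations and steroid increases "will be summarized, separately, by treatment group using frequency tables". SAP 1.1 says that the SAP "describes the implementation of the statistical analysis planned in the protocol".

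**The concern.** On both endpoints benefit means fewer events. A threshold on the pooled event rate therefore depends on the treatment effect: lowering the rate in the CMK389 arm lowers the pooled rate and makes it more likely that the comparison is not fitted. The rule can drop the analysis for a large benefit and keep it when there is none.

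The SAP's silence does not settle the matter. Because it presents itself as implementing the protocol, a programmer cannot tell whether the condition still applies. If it does not, the SAP's logistic model has no stated fallback for an arm with no events. What is at stake is whether a proof-of-concept study ends with an adjusted effect and interval for these endpoints, or only with counts.

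**Working it through.** **Arm sizes.** Protocol 3.1 and 11.7 give 66 randomised 1:1, 15% dropout and 28 per arm with Week 16 data: 66 × 0.85 = 56.1. The plan's only power figure confirms these sizes: SE = 9 × √(2/28) = 2.405; 5/2.405 = 2.079; Φ(2.079 − 1.282) = 0.787, against the stated approximately 80%. That figure concerns FVC and is not in dispute. I use 28 per arm for Week 16 deterioration and 33 per arm for steroid increase.

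**Threshold in events.** 0.20 × 56 = 11.2, so 12 events are needed. 0.20 × 66 = 13.2, so 14 are needed.

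**Direction.** At 1:1 the expected pooled rate is (p_placebo + p_drug)/2. If the drug prevented every event, this would reach 20% only for p_placebo of at least 40%.

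**Chance that the model is run.** P(X + Y ≥ threshold), with X and Y independent binomials, computed exactly. The event rates are assumptions, because the documents give none.

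| Placebo vs drug | 28 per arm | 33 per arm |
|---|---|---|
| 25% vs 25% | 78% | 80% |
| 25% vs 10% | 26% | 25% |
| 25% vs 5% | 12% | 10% |
| 30% vs 30% | 94% | 96% |
| 30% vs 10% | 45% | 45% |
| 40% vs 10% | 79% | 82% |
| 40% vs 20% | 95% | 96% |
| 50% vs 10% | 96% | 97% |

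With equal rates of 15% in both arms the model runs in only 13% (28 per arm) or 11% (33 per arm), so at low rates the rule mostly fails whatever the drug does.

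**Single results.**
- 11/28 vs 0/28: 11/56 = 19.6%, cancelled; two-sided Fisher p=0.0003.
- 10/28 vs 1/28: also 19.6%, cancelled; p=0.005.
- 13/33 vs 0/33: 13/66 = 19.7%, cancelled; p=0.00006.
- 6/28 vs 6/28: 12/56 = 21.4%, analysed, with no difference to find.

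**Cost in power.** As a yardstick I use a two-sided 5% Fisher test, which is not the plan's test, with 28 per arm. Power without and with the condition is 39% and 7% at 25% vs 5%; 33% and 18% at 30% vs 10%; 66% and 55% at 40% vs 10%; 89% and 86% at 50% vs 10%. With equal rates the condition can only remove rejections, so it does not raise the type I error.

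**Without the condition.** An ordinary logistic fit has no finite treatment odds ratio when one arm has no events. For the drug arm that probability is (1 − p)^n. With 33 per arm it is 0.90^33 = 3% and 0.95^33 = 18%; with 28 per arm, 5% and 24%.

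**The case against.** **The event rates may be high.** The composite is met by any one of four components, so its rate exceeds that of each alone. As an illustration, take the plan's SD of 9 and difference of 5. Assume normality, a baseline FVC of 75% predicted (so a 10% relative fall is 7.5 points), and an FEV1 component with the same SD and a correlation of 0.8. With arm means of −2.5 and +2.5, FVC and FEV1 alone give about 38% vs 19%, and the condition is met in about 91% of trials. With means of 0 and +5 they give about 27% vs 12%, and it is met in about 42%. DLCO and walk distance would raise both. This stands: a reader might infer that an effective drug will usually cancel its own comparison, and the documents do not support that as a general statement.

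**The SAP's event window is wider.** Counting a deterioration at any treatment visit raises the rate and shrinks the problem for that endpoint. This stands too. The point bears mainly on steroid increase, and on deterioration as the protocol defines it at Week 16.

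**The SAP model rarely loses the treatment effect.** A reader might infer that, once the condition is dropped, the logistic fit will often fail. Some coefficient may well be infinite if the azathioprine stratum is small and has no events, but the documents do not give that stratum's share. An empty stratum alone also leaves the treatment odds ratio finite, since that stratum then carries no information on treatment. Only an empty arm removes it, with the probabilities shown above.

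**Little is lost in a non-confirmatory trial.** A minimum-event rule before fitting a three-term model is ordinary practice. These endpoints are unpowered, the frequency tables are unconditional, and SAP 6.2.3 also models the components of deterioration as continuous variables. All true, and it limits the harm. It does not justify a pooled trigger that the treatment itself moves: sparse events call for a different estimator, not for dropping the comparison.

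**The SAP may already have superseded the rule.** It is based on the current protocol amendment and omits the condition. But it omits it silently while claiming to implement the protocol, so either reading can be defended.

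**Conclusion.** The point holds in a limited form. Protocol 11.5.1 makes two comparisons depend on an outcome that the drug is meant to lower, and the SAP neither applies nor withdraws that rule. This rests on reading the 20% as pooled over both arms, which is the plain sense of a sentence that names no arm.

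The size depends on event rates that the documents do not give. It is severe at placebo rates of about 20% to 40% with a strong effect, and small at 40% vs 20% or at 50% and above. The loss is the modelled effect and its interval for the affected endpoint. The counts by arm survive, and false-positive control is unharmed. If the SAP's unconditional model is the operative one, what remains is an unstated fallback for an arm with no events. The change is worth making because it is nearly free.

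**What to change.** Delete the 20% condition from Protocol 11.5.1, or state in SAP 6.2.3 that it is superseded. In the same paragraph, commit to reporting for each endpoint, whatever the event rate, the events by arm and a risk difference with a 95% confidence interval valid for sparse data, for example Miettinen-Nurminen. Keep the logistic model with its present terms, and prespecify a penalised (for example Firth) or exact version for the treatment odds ratio if an arm or stratum has no events. These named methods are reasonable choices, not the only correct ones. While editing, state whether the deterioration model uses Week 16 or any treatment visit, since the two documents differ.

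The cost is one or two SAP sentences and no new data. The intervals will be wide when events are few.

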#### 11.5.2 Safety

#### Vital signs

All vital signs data will be listed by treatment group, subject, and visit/time and if ranges are available abnormalities (and relevant orthostatic changes) will be flagged. Summary statistics will be provided by treatment and visit/time.

#### ECG evaluations

All ECG data will be listed by treatment group, subject and visit/time, abnormalities will be flagged. Summary statistics will be provided by treatment and visit/time.

#### **Clinical laboratory evaluations**

All laboratory data will be listed by treatment group, subject, and visit/time and if normal ranges are available abnormalities will be flagged. Summary statistics will be provided by treatment and visit/time.

#### 11.5.3 **Pharmacokinetics**

CMK389 plasma concentration data will be listed by treatment, and visit/sampling time point. Descriptive summary statistics will be provided by visit/sampling time point, including the frequency (n, %) of concentrations below the LLOQ and reported as zero.

For pharmacokinetic parameter determination, please see Section 8.7.

The descriptive statistics (n, mean, CV%, standard deviation (SD), median, geometric mean, geometric CV%, minimum and maximum) will be presented by time of dosing (1st to 4th dose) for all PK parameters of CMK389 except Tmax, where only n, median, minimum and maximum will be presented

# 11.5.4 Pharmacokinetic / pharmacodynamic interactions

Not applicable.

## 11.5.5 Other assessments

Commercially Confidential Information

# **11.7** Sample size calculation

We assume around 15% drop out, which should provide FVC data at week 16 from 56 patients (approximately 28 in each arm), if approximately 66 patients are randomized. Commercially Confidential Information

The sample size is determined by calculations with respect to the Bayesian analyses (Fisch et al 2014); based on uninformative priors) of the change from baseline in the percent predicted FVC after 16 weeks of treatment. This was derived via simulations using the QTD software. With 28 patients per group providing data at week 16 and assuming a standard deviation of 9% (Judson et al 2014), there is approximately 80% power to meet the efficacy criterion (posterior probability that CMK389 is better than placebo  $\geq 90\%$ ), if the true effect of CMK389 over placebo is 5%. Furthermore there is 10% probability of meeting the efficacy criterion if the true treatment difference is 0% (type I error rate).

